4.5 Endpoints

The following definitions of endpoints hold for all analyses described in this statistical analysis plan. For study participants, we define the study endpoint as 28 days after date of the Bamlanivimab infusion. This holds for both outcomes of COVID-related hospitalization with or without time consideration (i.e., no censoring vs censoring at Day 28). For example, if a study participant hasn't been hospitalized due to COVID-19 within 28 days after COVID-19 diagnosis, we'll treat the binary response of COVID-19 hospitalization as 0 without time consideration. However, with time consideration, it becomes right-censored since this participant may be hospitalized 29 or more days after COVID-19 diagnosis and our observation period is 28 days after COVID-19 diagnosis. More details are described in Section 5.8.1.3. For the pool of potential controls, we define the study endpoint as 28 days after a synthetic date of treatment. We will randomly select a number from the distribution of number of days after date of symptoms onset in study participants to identify an index date with which to define 28 days post infusion where we will monitor claims and EMR data for hospitalizations and mortality.

Commented [WWY14]: Should be the pool of controls which was before PS matching.

Figure 3 illustrates the timeline for study participants and controls to ensure alignment on an index date for symptoms onset and the follow-up period. Since the control group will not have an infusion date associated with them, we will randomly select a number from the distribution of number of days after date of symptoms onset in study participants to identify an index date with which to define 28 days post infusion where we will monitor claims and EMR data for hospitalizations and mortality.

[figure not shown]

Figure 3. Illustration of the timeline for study participants and controls.

For patients who do not experience a COVID-19 related hospitalization by Day 28 following the date of infusion or synthetic treatment, a censoring date is defined as the earliest of 28 days following the date of treatment, or for study participants, the early discontinuation date due to lost to follow-up.

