Commented [WWY34]: Suggest to be more specific for what will be test for non-parametric method

matching based sensitivity analyses will be performed to assess the numerical performances. In addition, propensity score subclassification (Rosenbaum, 1984) in conjunction with trimming strategy (Crump, 2009) will be adopted. Such greedy matching methods require a sizable (e.g., 70%) common support region for logit between treated and control, known as “overlap assumption”. It is possible that greedy matching excludes participants because treated cases fall outside the lower end of the common support region (those who have low logit) and nontreated cases fall outside the upper end of the common support region (those who have high logit). This can be investigated once we fit PSM model, estimate the logits, and plot them side-by-side for treated and control. If we see significant nonoverlap then we may need to try alternative such as trimming method.

One of the key limitations is - covariates in the propensity model may not be statistically significant resulting in suboptimal probability estimation of treatment assignments (or propensity scores).

5.8.1.3 Primary efficacy outcome analysis: COVID-related hospitalization rate at Day 28

Objective:	Data Variables:	Data Source:
Compare and determine if there is a significant difference in the rate of COVID-19 related hospitalization between study participants and matched controls	
 Flag of COVID-19 related hospitalization through Days 1-28 Flag of infusion treatment Demographics Elixhauser conditions 	
 Optum infusion pharmacy data UHC claims data CDSM COVID labs data BCRT COVID hospitalizations data Optum EMR data

Commented [XM35]: Please be specific which endpoint will be used for the primary analysis binary or time-to-event?

Commented [JAT36R35]: Specified in Section 4.5 Endpoint.

Commented [TEE37R35]: Added in parenthesis to further clarify in first sentence.

Commented [WWY38]: If add a table of Populations for Analyses, this table may not need (see attached sample SAP)

Commented [JAT39R38]: I added the table of populations for analyses in Section 5.1.1. but still want to keep the table with objective, data variables and data source here since they contain different information.

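### SAP 4.5's worked example counts 28 days from diagnosis although the endpoint is defined from infusion, and the onset-to-infusion timing analysis is written on the test-to-infusion gap

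*SAP*

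**What the plan says.** **Outcome window.** SAP 4.5 opens with "The following definitions of endpoints hold for all analyses described in this statistical analysis plan". For participants it says "we define the study endpoint as 28 days after date of the Bamlanivimab infusion", and applies this to the binary and the time-to-event outcome alike. For controls, "we define the study endpoint as 28 days after a synthetic date of treatment". The closing paragraph of the section anchors censoring the same way: "a censoring date is defined as the earliest of 28 days following the date of treatment", or earlier loss to follow-up for participants. The worked example between these statements describes a participant not "hospitalized due to COVID-19 within 28 days after COVID-19 diagnosis", codes that response 0, and then explains right-censoring: "this participant may be hospitalized 29 or more days after COVID-19 diagnosis and our observation period is 28 days after COVID-19 diagnosis".

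**Timing analyses.** SAP 5.12 and Protocol 6.5.6 each announce two analyses of infusion timing against hospitalization, one relative to the positive test and one relative to symptom onset. In both documents the method text of the second defines the gap as running from the COVID-positive date to the home infusion, exactly as in the first. The objective table in SAP 5.12 names the onset-to-infusion gap and lists the symptom onset date among the variables.

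**Onset date.** SAP 4.5 draws a "number of days after date of symptoms onset in study participants to identify an index date" for each control. How onset is dated is addressed in two margin replies in SAP 4.7. One says the test date will be used to approximate onset and to find controls infected at about the same time. The other says onset fields will be included if available, and places onset 2 days before diagnosis.

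**The concern.** SAP 4.5 is where a programmer would look for the coding rule. When a commenter on SAP 5.8.1.3 asked whether the primary endpoint was binary or time-to-event, the reply pointed to 4.5. Within that section, the worked example is the passage that shows when a patient without an event is coded 0 and when censored, and it uses the wrong start date. Following it would give participants a window starting at diagnosis while controls kept one starting at synthetic treatment. The added days before infusion are nearly event-free by construction, because current COVID-19 hospitalization is an exclusion criterion. The days lost at the end are genuine follow-up. Any distortion would therefore tend to favour treatment.

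The timing analysis raises a different problem. If the second analysis uses the first one's exposure variable, the onset-timing question is never examined and the report shows one result twice.

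The onset rule matters because it sets the controls' index date, and so their outcome window.

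**Working it through.** The plan gives no figure on this point to reproduce. The check compares the texts and then bounds the size.

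**1. Anchors, side by side**

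| Place | Start of the 28 days |
|---|---|
| SAP 4.5, participant definition | infusion |
| SAP 4.5, control definition | synthetic treatment date |
| SAP 4.5, censoring paragraph | infusion or synthetic treatment |
| SAP 5.8.1.3 table, "Flag of COVID-19 related hospitalization through Days 1-28", with Day 1 = infusion in SAP 4.2 | infusion |
| SAP mock Table A4 | treatment, real or synthetic |
| SAP mock Table A9, margin reply on coding the response 0 | treatment |
| SAP 4.5, worked example (three times) | diagnosis |

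Only the worked example departs from treatment as the anchor.

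**2. Size of the displacement if the example were coded**

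Let L be the days from diagnosis to infusion.

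- Post-infusion days inside the window = 28 − L.
- Share displaced = L / 28.
- SAP 4.2 allows up to 10 days from symptom report to infusion. If diagnosis could fall on the day of report, L runs from 0 to 10.
- If onset is set 2 days before diagnosis and the 10 days run from onset, L is at most 10 − 2 = 8.

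| L (days) | Post-infusion days | Share displaced |
|---|---|---|
| 0 | 28 | 0% |
| 8 | 20 | 8/28 = 28.6% |
| 10 | 18 | 10/28 = 35.7% |

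Controls keep 28 days throughout. These are shares of the window, not of events. Neither the distribution of L nor the timing of admissions is given, so no effect on the rate can be derived.

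**3. The two timing analyses**

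As written, both use gap1 = infusion date − positive test date, with the same outcome and methods. The exposures differ by 0 days for every participant, so the results are identical.

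Changing the wording to onset is not enough if onset is set at test − 2. Then gap2 = gap1 + 2, and

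logit = a + b·gap1 = (a − 2b) + b·gap2.

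The slope and its p-value are unchanged; only the intercept moves. In a simulated illustration (1,000 participants, gaps of 0 to 8 days), slope 0.1053 and p = 0.0028 came out both ways. The intercept went from −2.2007 to −2.4113, which is −2.2007 − 2 × 0.1053.

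Grouped results could differ, but only through the cut-points. A cut at 4 days or fewer splits gap1 into 0–4 and 5+. The same cut on gap2 splits gap1 into 0–2 and 3+. A cut at 6 or fewer on gap2 restores 0–4 and 5+.

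**4. The onset rule and the control index date**

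Take the test date as the diagnosis date, and let d be a participant's days from symptom report to test.

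- Test − 2 in both arms: (test − 2) + (L + 2) = test + L. The control's index date is its own test date plus a drawn test-to-infusion gap.
- First report for participants, test − 2 for controls: (test − 2) + (L + d) = test + L + (d − 2).

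For assumed values d = 1, 2 and 4, the mixed rule moves the control's index date by −1, 0 and +2 days.

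**The case against.** The strongest reply is that these are drafting slips whose intent is plain. On the window, the definition, control window, censoring paragraph, primary-analysis table and mock Table A4 all point to treatment. The margin reply at mock Table A9 restates the same coding rule with the correct anchor. Harm requires someone to follow an illustration over all of these. L = 10 is also an extreme, since the home-testing route needs a kit to be completed and returned before confirmation.

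On timing, the lead sentences in both documents, and the objective row and variable list in SAP 5.12, show that onset was meant, and the analysis lies outside the primary, exploratory and safety objectives.

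On the onset rule, Figure 3 of the SAP is not in the available text and may show more about onset.

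Much of this stands. The endpoint is not undefined, the 36% is an outer bound, and the efficacy conclusion does not rest on the timing analyses. The Table A9 reply strengthens the case for correcting the example. What does not stand is that clear intent makes correction unnecessary. The method sentence of a pre-specified analysis names the wrong variable in two documents. The margin-note approximation would also leave the continuous model a duplicate after a simple change of wording. The caveat about Figure 3 is fair, and the onset rule is the minor part of this point.

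**Conclusion.** Both main parts hold and should be corrected.

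- **Window.** The worked example in SAP 4.5 contradicts the governing definition. Coded literally, it would displace 0 to 10 days of participants' follow-up (0–36% of the window), or 0 to 8 days (0–29%) under the 2-day offset, with no matching shift in controls. The direction would tend to favour treatment; the effect on the hospitalization rate is not computable and may be zero. The ranges rest only on the 10-day limit and the 2-day approximation.
- **Timing.** As written, the second timing analysis repeats the first. The onset question goes unanswered, but the efficacy conclusion is unaffected.
- **Onset rule (minor).** In the text available, the approximation appears only in margin replies, without saying whether it covers participants, controls or both.

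**What to change.** 1. In SAP 4.5, change the three references to diagnosis in the worked example so that the 28 days run from infusion.
2. In SAP 5.12 and Protocol 6.5.6, define the second gap as the date of first symptom report in ProtectWell to the date of infusion. Do not use diagnosis minus 2 for participants here, because it only shifts the first gap by a constant.
3. Move the onset approximation into the SAP body. State whom it covers and which onset date sets the controls' synthetic date. Use the same rule when drawing the gap from participants and when applying it to controls. If that rule is test minus 2 in both arms, say that it amounts to adding a drawn test-to-infusion gap to the control's test date.

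The cost is three phrases in SAP 4.5, one method sentence in each document, and one or two sentences moved into the SAP body. No new data collection is needed: first symptom report, test date and infusion date are already collected. The changes should be made before outcome data are accessed.

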4.4 Study Population

4.4.1 Selection Criteria

Both study participants and matched controls will meet the inclusion and exclusion criteria below.

Inclusion Criteria:

- Age 65+, confirmed SARS-CoV-2 positive, located in an area where Bamlanivimab (LY3819253) is available for infusion
- Have mild or moderate COVID-19 symptoms (after stage 1 of symptom tracking)

Commented [JAT4]: Update to keep the same criteria in the latest protocol (version 10 on Feb 3, 2021).

Commented [JAT5]: Remove it as it is no necessary for active participants and controls.

- Control only: Confirmed symptomatic COVID-19 through Optum EMR data.

Exclusion Criteria:

- Current (from first symptom report) hospitalization for COVID-19
- Prior administration of Bamlanivimab

Commented [JAT6]: Remove as not necessary per the EUA.

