5.1.1 Populations for Analyses

We define the analysis populations in Table 3 along with the analysis we will conduct. All patients meet the study eligibility criteria. Note that all populations for analyses are UHC members, and the following proposed analytical methods are for UHC members. We may see non-UHC members satisfying the study eligibility criteria, but we cannot obtain or have very limited information of their comorbidities, demographic (e.g., area of residence, socioeconomic index), and if having immunosuppressive treatment prior to COVID-19 diagnosis.

Table 3. Population for analyses

Population	Data for analysis	Definition/Data
Study participants	Disposition analysis and safety	Study participants who sign informed consent and receive Bamlanivimab in single infusion of 700 mg.
Pool of potential controls	Formation of the control group Pre-matching identification of risk factors Estimation of prognostic scores	Patients who meet the study eligibility criteria but did not receive Bamlanivimab.

Commented [WWY23]: Would suggest to revise to include general results reporting, definition of the analysis populations, analysis methods, definition of baseline Refer to attached sample SAP

Overall population	Descriptive analyses Propensity score matching	Consists of study participants and pool of potential controls.
Propensity score matched population	Efficacy and descriptive analyses	Subset of the overall population consisting of study participants and matched controls after propensity matching.
Double score (propensity score and prognostic score) matched population	Sensitivity analyses	Subset of the overall population consisting of study participants and matched controls after double matching.

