5.8.1 Main analytical approach

5.8.1.1 Pre-matching identification of risk factors as matching covariates

Before matching, we will select covariates to be included in the propensity score estimation model. Covariates that are predictive of both treatment status and the outcomes and covariates that are associated with the outcomes will be selected to estimate propensity score. To do so, we will first conduct a literature review to identify the risk factors that are associated with COVID-19 hospitalization. The findings from the literature review will help create a list of variables on which treatment and control groups will be matched.

Consider a binary response taking a value of 1 if a patient is hospitalized due to COVID-19, and 0 if a patient is tested positive for SARS-CoV2 but does not have a record of subsequent COVID-related hospitalization (hospitalization within 38 days of a positive test). We include risk factors such as demographic (e.g., gender, age, race, geographical area such as state or county), comorbidities (Elixhauser scores related comorbidities such as diabetes, metastatic cancer, heart diseases, obesity, coagulopathy, and so on), and other potential clinical attributes as available in

the identification of the appropriate matched cohort. These risk factors will also include all clinically identified variables by Eli Lilly to define moderate and high-risk groups. We will run this step three times with three datasets; specifically, we consider:

- a. Iteration 1: This is based on retrospective data available in-house consisting of Medicare Advantage (MA) members, aged greater than or equal to 65, and COVID diagnosed. We will exploit BCRT, CDSM, and UHC Claims data sources. The study cohort here is a broader population than the study participants.
- b. Iteration 2: This is solely based on data associated with study participants. We will exploit risk factors from UHC Claims and study enrollment information from Optum infusion pharmacy data.
- c. Iteration 3: This is based on information of both the general MA population and study participants –retrospective and prospective data in Iteration 1 and Iteration 2, respectively. We will exploit COVID labs and hospitalizations from BCRT and CDSM, risk factors from UHC Claims data, and study enrollment information from Optum infusion pharmacy data.

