6.3 Appendix 3: Mock TFLs

Tables:

Table A4. Characteristics of study participants and the pool of potential controls. For notation, n indicates the cohort size (i.e., number of subjects); IQR is interquartile range; SD is standard deviation; % indicates percentage.

Characteristics	Study participants ($n =$)	Pool of potential controls ($n =$)	p-value (study participants vs pool of potential controls)
Age: median (IQR) or mean (SD)			
Age: n (%)			
65-			
65 – 69			
70 – 74			
75 – 79			
80+*			
*: We can separate 80+ into finer groups as needed.			
Gender: n (%) in female			
Race: n (%)			
White			
Black			
Asian			
Hispanic			
Other			
Urbanization of residence: n (%)			
Urban			
Suburban			
Rural			

Commented [XM55]: Please add footnotes for each table, such as abbreviation, test for p-value, model specification and locations for:
 Dataset: dataset location/dataset name.sas7bdat
 Program: program location/program name.sas
 Output: output location/output name.rtf

Commented [XM56]: Would separate this table into two tables – before and after PS match, since there may be study participants could not find matched control

CONFIDENTIAL

[Protocol number: UHG (J2X-NS-I002)] SAP [v.3]

Socioeconomic index: median (IQR) or mean (SD)	
Dual status: n (%) With Medicaid Elixhauser comorbidity score: median (IQR) or mean (SD)	
Elixhauser conditions*: n (%) *: There are 29 conditions in total as shown in Table A1.	
Immunosuppressive treatment 6 months prior to date of COVID diagnosis: n (%)	
Stay in nursing facility during COVID test*: n (%) *: This availability depends on the claims lag. We may have partial information from the BCRT data but it's only COVID related and doesn't cover a stay of nursing facility due to other reasons.	
COVID-related hospitalization during Days 1-28 after the treatment (i.e., Bamlanivimab infusion for study participants, synthetic treatment for control candidates and matched controls): n (%)	

LY3819253

Dataset: dataset location (data table name with the corresponding database in Google BigQuery)

Program: program location/program name.R

Output: output location/output name.csv or .xlsx

Repeat Table A4:

Table A4.2

Patient demographics and other baseline characteristics

Propensity score matched population

Programming notes:

Replace “study participants” with “study participants after propensity score matching” and replace “the pool of potential controls” with “matched controls” in the header.

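### Controls are not required to be alive and un-admitted on their synthetic treatment date, so the two groups are not at risk on the same terms at time zero

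*SAP*

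**What the plan says.** **Index date.** Controls have no infusion, so SAP 4.5 (and Protocol 6.5) will "randomly select a number from the distribution of number of days after date of symptoms onset in study participants to identify an index date". SAP 4.2 allows up to 10 days from symptom report to infusion; the distribution of that lag is not given. An author reply in the margin of SAP 4.7 approximates onset as two days before the COVID-19 diagnosis date.

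**Outcome window.** For the control pool, SAP 4.5 says "we define the study endpoint as 28 days after a synthetic date of treatment". Mock Table A4 in SAP 6.3 has the matching row: "COVID-related hospitalization during Days 1-28 after the treatment (i.e., Bamlanivimab infusion for study participants, synthetic treatment for control candidates and matched controls". SAP 5.8.1.3 and 5.8.2 also describe the outcome over Days 1 to 28. Two sentences in SAP 4.5 are looser. A worked example for a participant says "our observation period is 28 days after COVID-19 diagnosis". The censoring rule begins "For patients who do not experience a COVID-19 related hospitalization by Day 28 following the date of infusion or synthetic treatment", with no lower limit on the event date.

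**Eligibility.** SAP 4.4.1 applies the same criteria to participants and controls, including the exclusion "Current (from first symptom report) hospitalization for COVID-19". Table 3 in SAP 5.1.1 defines the pool as "Patients who meet the study eligibility criteria but did not receive Bamlanivimab", without saying on which date eligibility is judged. On vital status, SAP 4.2 says only that controls may die after the synthetic date.

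**The concern.** A participant reports symptoms, receives a kit, tests positive and is visited at home, and must be alive and out of hospital throughout. That condition holds at the participant's time zero by design. A control's time zero is a calculated date, and no text shown requires the control to be at risk on it or says whether to exclude, redraw or keep a control whose date falls after an admission or death.

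The case can easily arise. The EMR that confirms a control's symptoms also supplies the control's test and admission (SAP Table 1), and nothing bars a control whose positive test was taken on admission. If the margin note's approximation is used, that control's onset is set two days before admission, and any drawn lag longer than two days puts the index date after the admission.

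At stake is the primary comparison. A person who could not have been a participant contributes to the control rate, and the direction of the error depends on which sentence the programmer follows. The E-value and the proportion of unmeasured confounding in SAP 5.8.2 are not aimed at a time-zero error.

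**Working it through.** **The plan's own figures.** The documents give no figure for this point, so I first checked that I read the SAP's rates as intended. Table 2, 25% control rate, 75% reduction (6.25%), two-sided 5%, 90% power:

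- n′ = [1.96·√(2·0.15625·0.84375) + 1.2816·√(0.25·0.75 + 0.0625·0.9375)]² / 0.1875² = 76.7 per group.
- With continuity correction: n = (n′/4)·[1 + √(1 + 4/(n′·0.1875))]² = 87.05 per group, or 174.1 in total. Rounded up, this is the stated 175.

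The other nine rows agree to within one patient. For the reduced size of 1,000 per group, SAP 4.4.2 plans for 15% against 10%, a risk ratio of 0.67. The 15% rate is used below.

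**Calculation 1: assumed share before the index date.** Let R = 0.15 be a control's risk from onset to Day 38, and f the share of those admissions that precede the index date. Taking 15% for this longer window is an assumption, since the SAP's rate is for Day 28 after the index date. The values of f are also assumed. With no treatment effect:

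- Correct rate, people at risk at index only: R(1−f)/(1−Rf). Participants show this rate.
- Control rate if earlier admissions are kept as non-events: R(1−f). Risk ratio = 1/(1−Rf).
- Control rate if they are counted as events: R. Risk ratio = (1−f)/(1−Rf).

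| f | Correct rate | Control rate, non-events | RR, non-events | RR, counted |
|---|---|---|---|---|
| 10% | 0.1371 | 0.135 | 1.015 | 0.914 |
| 20% | 0.1237 | 0.120 | 1.031 | 0.825 |
| 30% | 0.1099 | 0.105 | 1.047 | 0.733 |
| 40% | 0.0957 | 0.090 | 1.064 | 0.638 |

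**Calculation 2: constant hazard.** Set λ = −ln(0.85)/28 = 0.0058 per day, so that the 28-day risk after the index date is 15%. Give every control the same lag g (assumed). Then P = 1 − exp(−λg) is the risk before the index date. The control rate is 0.15(1−P) if those admissions are kept as non-events and P + 0.15(1−P) if they are counted. Rejection chances use a two-sided 5% test of two proportions with 1,000 per group (0.025 nominal in each direction).

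| g (days) | P | RR, non-events | RR, counted | Chance of a false benefit, counted | Implied f |
|---|---|---|---|---|---|
| 2 | 0.0115 | 1.01 | 0.94 | 0.09 | 7% |
| 3 | 0.0173 | 1.02 | 0.91 | 0.15 | 10% |
| 5 | 0.0286 | 1.03 | 0.86 | 0.31 | 16% |
| 7 | 0.0398 | 1.04 | 0.82 | 0.53 | 22% |
| 10 | 0.0564 | 1.06 | 0.76 | 0.81 | 28% |

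Implied f is P/[P + 0.15(1−P)]. With non-events, the chance of a false finding against treatment rises only from 0.025 to between 0.032 and 0.077.

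**With an at-risk rule.** Both groups show 15%, the risk ratio is 1.00, and rejection is 0.025 in each direction. The sample size figures do not change.

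**The case against.** The defense has real strength. The hospitalization exclusion does apply to controls, and read broadly it could run from onset up to the index date. The remark that controls may die after the synthetic date implies that they are alive on it. Random draws reproduce the participants' lag distribution on average, and McNemar's test does not need both members of a pair to start on the same day of illness. SAP Figure 3, which illustrates the alignment, is not shown here and may carry a rule.

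A reader might go further than the text allows in three ways.

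- *That the plan counts pre-index admissions as control events.* The control endpoint in SAP 4.5 and the row in Table A4 both start at synthetic treatment, so on the main definition these admissions are not events. The diagnosis-anchored example is written for a participant, and an event by Day 28 following the synthetic date most naturally means one after it.
- *That the wording "hospitalization within 38 days of a positive test" sets the control outcome.* It stands in SAP 5.8.1.1 and defines the response for the model that selects matching covariates. It is not the efficacy endpoint.
- *That the bias could by itself produce the planned effect of 0.67.* Among the assumed shares, only 40% passes that value, and only if the admissions are counted. Under a constant hazard, even a 10-day lag for every control gives a share of 28%; 40% would need admissions concentrated soon after onset.

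What remains is that the exclusion is tied to an event that controls do not report, no date of assessment is given for them, and an implication about survival is not a selection rule.

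**Conclusion.** The point holds as a gap in the definition of time zero. The text shown does not require a control to be un-admitted on the synthetic date, while participants meet that condition by design. The reading closest to the SAP keeps such controls as non-events, which gives a small bias against treatment: a no-effect risk ratio of about 1.02 to 1.06 for assumed shares of 10% to 40% of a 15% onset-to-Day-38 risk. The larger bias, in favor of treatment (about 0.91 to 0.73 for assumed shares of 10% to 30%), arises only if the looser sentences in SAP 4.5 are followed.

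Both ranges rest on assumptions about the lag and the timing of admissions, which the documents do not give; an early peak in admissions would enlarge either bias. This should be corrected before outcome data are accessed, because it affects the primary comparison and costs little to put right.

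**What to change.** In SAP 4.5 and Table 3:

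1. Require each control to be alive on the synthetic date and not admitted for COVID-19 between onset and that date. Replace a control who fails with the next-nearest eligible one.
2. Count only admissions on Days 1-28 after the index date, in the binary and time-to-event analyses alike, and say how an admission on the index date itself is classed.
3. Reconcile the diagnosis-anchored example and the open-ended censoring sentence in 4.5 with the row in Table A4.
4. Report the number of controls removed, for example as an added row in Table A7.

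Preferably give each candidate control the lag of the participant to whom it would be matched, and check that it is at risk on that date during matching. If controls are removed after a random draw, long lags are lost more often, because they leave more time for an admission, and the control lags shift shorter than the participants'.

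No further condition on Bamlanivimab is needed, since Table 3 already limits the pool to untreated patients. The cost is some SAP wording, one programming step and slightly fewer eligible controls.
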